## Dose of study drug -

Low dose 100 mg/kg/day Medium dose 200 mg/kg/day High dose 300 mg/kg/day

[figure not shown]
**When to start study drug -** Study drug will be started when infant has been off of TPN for at least 3 days so that IV arginine in TPN does not interfere.

**Sample collection** - 1 mL of blood will be collected from each subject at 2 time points: before starting citrulline (Day 0) and then after completing 1 week enteral L-citrulline supplementation (Day 7). Discarded blood sample from routine blood draw will be used.

It is standard of care for all preterm infants to get weekly blood draws on Tuesdays for hemoglobin monitoring. We will use discarded blood sample from the Tuesday after being on full feeds (no TPN) and start enteral L-citrulline supplementation on the first Tuesday (Day 1) after off TPN for at least 3 days. After 1 week, supplementation will be discontinued (last dose Monday PM) and discarded blood sample from Tuesday (Day 7) will be used to analyze plasma levels or L-citrulline and L-arginine. Immediately after blood collection, blood will be centrifuged at 4-degree C to extract serum. Serum will be divided into aliquots of 100 microliter & stored at -80-degree C for future use.

1 mL of urine will be collected before starting (Day 0) and then daily thereafter till the last day of L-citrulline supplementation (Day 7). Urine will be collected by placing cotton balls in diapers at around noon  $\pm$  2 hours (in between the 2 doses of study drug).

All sample collection will be part of routine/standard care of the infant and no extra blood draws/invasive procedures will be needed.

Sample collected - (time points)

- \*Discarded blood (for arginine, citrulline & ADMA)
- ^Urine daily for urinary arginine, citrulline, nitrites and nitrates

**\*Enteral L-citrulline** –low, medium or high dose divided into 2 doses via gavage feeding tube i.e. 10% L-citrulline twice daily.

**Measurements:** 

**Serum L-citrulline & L-arginine measurement** - We will measure amino acids (AA) in serum using an HPLC-MS approach. A cocktail of stable-isotope enriched AA will be added to serum samples & AA will be extracted using a solid-phase cartridge. Extracted AA will be separated by HPLC (C-18 Colum) eluted with a methanol ammonium formate gradient. AA will be injected directly into a QTRAP 6500 instrument tuned for low mass analyses. AA will be detected using characteristic fragmentation ions. Concentrations of AA in the original sample will be determined by co-paring peak areas to those of the stable isotope-enriched internal standards. For this initial study, we will measure citrulline & arginine.

**Urinary nitrates and nitrite measurement (metabolites of NO)** - Urinary nitrite, nitrate and creatinine will be measured by GC-MS following conversion to the pentafluorobenzyl derivatives.

### 6.0 Study Product Description

Information in this section can usually be obtained from the IB or the package insert.

### Formulation, Packaging, and Labeling

### **Product Storage and Stability**

Keep container dry. Keep in a cool place. Ground all equipment containing material. Keep container tightly closed. Keep in a cool, well-ventilated place. Combustible materials should be stored away from extreme heat and away from strong oxidizing agents.

Precautions: Keep away from heat. Keep away from sources of ignition. Empty containers pose a fire risk, evaporate the residue under a fume hood. Ground all equipment containing material. Do not breathe dust. Wear suitable protective clothing in case of insufficient ventilation, wear suitable respiratory equipment If you feel unwell, seek medical attention and show the label when possible. Avoid contact with skin and eyes

## Dosage, Preparation and Administration of Study Intervention/Investigational Product

A 10% L-citrulline solution will be prepared using the powdered product by adding 10 g of powder in 100 ml of distilled water (each ml = 100 mg). Doses prepared will be determined by the study group assignment. For e.g., for a 2 Kg infant in Group 1 (50 mg/kg dose = 1 ml). Doses will be administered twice daily.

Safety precautions: Gloves Splash goggles, lab coats, dust respirators and gloves should be used while preparing the doses. Avoid direct contact with skin. Prepared solutions can be held in a cool place for a maximum of 24 hours.

## Modification of Study Intervention/Investigational Product for a Participant

No dose modifications will be done for specific lab values. In case of toxicity, study will be aborted as discussed in section 7.0 below.

# Accountability Procedures for the Study Intervention/Investigational Product(s)

Study drug (L-citrulline) will be bought from the vendor (Vitaflo) by the PI. The product will be shipped at one time. About 300 g of product will be needed for this study. Unused product will be in the investigational pharmacy for future studies.

# Assessment of Subject Compliance with Study Intervention/Investigational Product

Since all doses will directly be administered by the bedside nurse, non-compliance is not applicable to this study. Subjects must receive 12/14 doses to be considered a complete subject.

# **Concomitant Medications/Treatments**

There will be no medication or treatment restrictions during this study. All premature infants will continue to receive standard of care treatment.

## 7.0 Adverse Events or Unanticipated Problems involving Risk to Participants or Others

Immediate risks: Increased NO production may theoretically lead to systemic hypotension – all these infants will be in an intensive care setting with cardiac monitors and continuous blood pressure monitoring. Significant hypotension will be defined as a 25% drop in systemic mean blood pressure from baseline (average mean arterial pressure in the week prior to starting study drug).

Local irritation to skin or eyes is possible with direct contact with study drug.

Long-range risks: A theoretical risk of adverse impact on structural remodeling of pulmonary architecture vis increase in arginase two expression in lungs (seen in rats).

### Rationale:

Children with urea cycle defects have been treated with L-citrulline for decades and showed no evidence of toxicity. Previous studies in literature have not reported any significant adverse effects. The benefit of treatment (helping treat or prevent BPD\_PH) far outweighs the risks since this condition is associated with significant morbidity/mortality and no preventative measures exist at this time. The study drug has already been tested on animal models and there are no alternatives to studying the safety, efficacy and dosing in preterm infants.

ICH E6 defines an AE as any untoward medical occurrence in a patient or clinical investigation subject administered a pharmaceutical product regardless of its causal relationship to the study treatment. An AE can therefore be any unfavorable and unintended sign (including an abnormal laboratory finding), symptom, or disease temporally associated with the use of medicinal (investigational) product.

All AEs including local and systemic reactions not meeting the criteria for "serious adverse events" should be captured on the appropriate CRF. Information to be collected includes event description, time of onset, clinician's assessment of severity, relationship to study product (assessed only by those with the training and authority to make a diagnosis, which would include MD, PA, Nurse Practitioner, DO, or DDS), and time of resolution/stabilization of the event. All AEs occurring while on study must be documented appropriately regardless of relationship. All AEs will be followed to adequate resolution.

Any medical condition that is present at the time that the patient is screened will be considered as baseline and will not be reported as an AE. However, if it deteriorates at any time during the study, it should be recorded as an AE.

All AEs must be graded for severity and relationship to study product.

**Severity of Event:** All AEs will be assessed by the clinician using a protocol defined grading system. For events not included in the protocol defined grading system, then the following guidelines will be used to quantify intensity.

- Mild: events require minimal or no treatment and do not interfere with the patient's daily activities.
- Moderate: events result in a low level of inconvenience or concern with the therapeutic measures. Moderate events may cause some interference with functioning.

- Severe: events interrupt a patient's usual daily activity and may require systemic drug therapy or other treatment. Severe events are usually incapacitating.
- Life threatening: any adverse drug experience that places the patient or subject, in the view of the investigator, at immediate risk of death from the reaction as it occurred, i.e., it does not include a reaction that had it occurred in a more severe form, might have caused death.

Changes in the severity of an AE should be documented to allow an assessment of the duration of the event at each level of intensity to be performed. Adverse events characterized as intermittent require documentation of onset and duration of each episode.

Protocol Grading System for Hypotension:

Mild: Drop in systemic mean arterial pressure (MAP)  $\leq$  10% from baseline

Moderate: Drop in systemic mean arterial pressure (MAP)  $\leq$  25% from baseline

Severe: Drop in mean arterial pressure (MAP) > 25% from baseline

Life threatening: Severe hypotension requiring 2 or more inotropes (Dopamine, Epinephrine, Norepinephrine)

**Relationship to Study Products:** If there is any doubt as to whether a clinical observation is an AE, the event will be reported. All AEs must have their relationship to study product assessed using the terms: associated or not associated. In a clinical trial, the study product must always be suspect. To help assess, the following guidelines are used.

- Associated The event is temporally related to the administration of the study product and no other etiology explains the event.
- Not Associated The event is temporally independent of study product and/or the event appears to be explained by another etiology.

**Serious Adverse Event (SAE)**: An SAE in our study will be defined as an AE that meets one of the following conditions:

- Death during the period of protocol defined surveillance
- Life-threatening event (defined as a subject at immediate risk of death at the time of the event) significant hypotension requiring 2 or more inotropes

- Results in a persistent or significant disability/incapacity: Intraventricular hemorrhage Grade III or more, Necrotizing enterocolitis requiring surgery, Retinopathy of prematurity requiring surgery
- Significant lab abnormalities: Thrombocytopenia < 50,000

All SAEs will be:

- recorded on the appropriate SAE CRF
- followed through resolution by a study clinician
- reviewed and evaluated by a study clinician

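### The adverse-event baseline is fixed at screening, but dosing starts later, so a condition that arises between the two can be recorded as an on-study adverse event

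*Combined protocol and SAP*

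**What the plan says.** Section 7.0, under Rationale, sets the reference point for adverse events: "Any medical condition that is present at the time that the patient is screened will be considered as baseline and will not be reported as" adverse events. It continues: "However, if it deteriorates at any time during the study, it should be recorded as an AE". It also requires that "All AEs occurring while on study must be documented appropriately regardless of relationship". The visible text does not say when being on study begins for this purpose.

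The same section takes its general AE definition from ICH E6, as an occurrence in a patient or "subject administered a pharmaceutical product regardless of its causal relationship to the study treatment".

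For hypotension alone, the opening of section 7.0 gives a different reference point: "baseline (average mean arterial pressure in the week prior to starting study drug").

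Section 5.0 fixes the start of dosing: "Study drug will be started when infant has been off of TPN for at least 3 days". The sample-collection text places Day 1 on the first Tuesday that meets this condition. Being off TPN is not an entry criterion in section 3.0. Section 4.0 has parents approached a second time 24 to 48 hours after the first discussion. Section 5.0 (Dispensing) has the dose group assigned after enrolment and before drug is dispensed, so an infant can belong to a group before receiving any dose.

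**The concern.** Aim 2 is the safety of a product that, according to section 1.0, has not been studied in preterm infants. There is no untreated arm to show the background rate of complications of prematurity, so the AE and SAE rates in the three dose groups will be read largely in absolute terms. With 14 infants per group, one affected infant moves a group's rate by 1/14, or about 7 percentage points.

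The screening baseline does not mark the start of exposure. An oxygen increase, a metabolic abnormality, a platelet fall or an intraventricular haemorrhage that begins after screening and before the first dose falls outside the baseline rule. If it is recorded, nothing in the visible text says to keep it apart from events that follow dosing. Blood pressure has its own pre-dose reference. The other items named under Aim 2 (oxygen and respiratory support, metabolic findings, blood counts) do not.

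**Working it through.** **The plan's own safety figure.** Section 4.0 states power 0.92 for an equivalence test with 11 per group, SD 10 mmHg, limits ±15 mmHg, true difference 0 and level 0.05. For two one-sided t tests, df = 2 × 11 − 2 = 20 and the standard error is 10 × √(2/11) = 4.26 mmHg. Integrating over the distribution of the sample variance gives 0.920, so the figure reproduces. It concerns blood pressure, which has a pre-dose baseline, and this point does not affect it.

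**The rules side by side.**

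| Item | Reference point | Place |
|---|---|---|
| AE baseline | screening | 7.0, Rationale |
| Worsening of a baseline condition | any time during the study | 7.0, Rationale |
| General AE definition | subject given a product | 7.0, Rationale |
| Hypotension baseline | week before study drug | 7.0, opening |
| First dose | first Tuesday after at least 3 days off TPN | 5.0 |

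The first two rows are anchored to screening or study entry, the next two to exposure. They agree only if screening and first dose coincide, and the plan does not require that.

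**How long the gap could be.** If TPN stops on a Saturday, the next Tuesday is day 3. If it stops on a Sunday, that Tuesday is only day 2, so dosing waits until day 9. The interval from end of TPN to first dose is therefore 3 to 9 days. The gap from screening to first dose is longer if the infant is screened while on TPN, and can be shorter if screened after TPN has stopped. The documents do not say which.

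**Share of events before dosing (illustration).** Assume a constant daily event rate, a gap of g days, and recording to the end of 7 days of dosing. The share is g/(g + 7):

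- 1 day: 1/8 = 13%
- 2 days: 2/9 = 22%
- 3 days: 3/10 = 30%
- 9 days: 9/16 = 56%
- 21 days: 21/28 = 75%

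With baseline at first dose, the share in the treatment-emergent count is 0% by definition.

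**Counts per group (illustration).** Assume a daily risk of 1% and 14 infants. The expected number with a pre-dose event over 9 days is 14 × (1 − 0.99⁹) = 1.21. During 7 days of dosing it is 14 × (1 − 0.99⁷) = 0.95. A 2-day gap gives 14 × (1 − 0.99²) = 0.28.

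**Effect on a dose comparison (illustration).** Suppose one dose doubles the on-drug daily risk to 2%: 14 × (1 − 0.98⁷) = 1.85. On dosing-period events the ratio between groups is 1.85/0.95 = 1.95. With the 9-day pre-dose events added to both groups it is (1.85 + 1.21)/(0.95 + 1.21) = 3.06/2.16 = 1.42. The ratio shrinks toward 1 and both absolute counts rise.

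**The case against.** The strongest reply is that the AE definition already settles the matter: an illness that begins before any product is given does not occur in a subject given the product, so it is not an AE, and the duty to document AEs covers only events that meet the definition. On this view the screening sentence only says what is left out. Time of onset goes on the CRF, and the relationship rule would class a pre-dose event as not associated. Section 8.0 discontinues infants who develop an exclusion criterion, so some would never be dosed.

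Much of this stands. A reader might infer that pre-dose illnesses are in fact counted against a dose group. The documents do not say so, and section 9.0 specifies no AE table by dose. Recorded onset times would also allow later separation.

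It does not remove the conflict. If AEs could only follow dosing, the natural baseline would be first dose, yet the stated one is screening. Section 7.0 also says that doubtful observations are to be reported, and documentation is required whatever the relationship. Section 8.0 sends the safety data of withdrawn subjects to the DSMB, with no exception for infants never dosed. Onset times make separation possible, but no rule calls for it.

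A reader might also infer from a listed SAE such as "Retinopathy of prematurity requiring surgery" that late events will be missed after 7 days of dosing. The documents do not support that conclusion: the text of section 7.0 available for review is incomplete, and the surveillance period may be defined in the part not seen.

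**Conclusion.** The point holds as a conflict between stated rules. The AE baseline is anchored to screening, while the AE definition beside it and the blood-pressure baseline are anchored to exposure. Read literally, a condition that starts or worsens before first dose can enter the record as an on-study AE or SAE.

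The expected harm is inflated absolute AE rates and weaker contrast between doses. Assignment by sequence does not depend on illness, so bias toward one dose is not expected.

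The size cannot be fixed from the documents. The 13% to 75% range for gaps of 1 to 21 days rests on an assumed gap, a constant event rate and recording that ends with dosing. A longer recording window lowers the share; a higher event rate in the earlier days raises it. It would go too far to say that most reported AEs must precede the drug, because that requires a gap of more than 7 days, which the documents neither state nor exclude. Hypotension is not affected. The change is worth making because Aim 2 is safety, groups are small and no arm is untreated.

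**What to change.** In section 7.0 (Rationale):

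1. Define AE baseline as the infant's status at first dose, in line with the pre-dose reference already used for blood pressure.
2. Count as treatment-emergent only events that start or worsen after the first dose.
3. List events between consent and first dose separately, outside any AE summary by dose. This moves them out of the summaries, not out of the record or out of any reporting that the IRB or DSMB requires.

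The cost is a wording change, one check of the infant's chart at first dose and one additional listing. No stated sample size or power figure changes.

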# Procedures to be Followed in the Event of Abnormal Laboratory Test Values or Abnormal Clinical Findings

## **Reporting Procedures**

Discarded blood samples from routine blood draws will be used for study measurements. No extra blood will be drawn from infants. This study does not involve any invasive procedures.

Any AE considered serious by the PI or Sub investigator or which meets the aforementioned criteria must be submitted on the SAE form to the IRB in accordance with IRB policies and procedures.

The study clinician will complete a Reportable Event Form within the following timelines:

- All serious adverse events described above to the UTMB IRB will be reported via InfoED utilizing the Reportable Event Form within 10 days.
- Serious adverse events involving an unexpected death or life-threatening experience related to research which be reported to the UTMB IRB within 2 days after first knowledge by the principal investigator.

All SAEs will be followed until satisfactory resolution or until the PI or Sub investigator deems the event to be chronic or the patient to be stable.

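### Adverse events other than hypotension are graded on anchors that largely do not fit preterm infants in intensive care, and the two-category causality rule, which covers all events, leans towards not associated

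*Combined protocol and SAP*

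**What the plan says.** Aim 2 (Section 2.0) is to determine safety. Its main measure is hypotension. It also lists higher oxygen need or respiratory support, metabolic abnormalities and blood-count effects as parameters to record. Section 9.0 makes safety a secondary outcome.

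Section 7.0 requires each adverse event to receive a severity grade and an attribution. The only event-specific scale is headed "Protocol Grading System for Hypotension". For the rest: "For events not included in the protocol defined grading system, then the following guidelines will be used to quantify intensity". The general grades are:

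- Mild is defined by treatment and activity together: "events require minimal or no treatment and do not interfere with the patient's daily activities". No example is given.
- The next grade up, moderate, is worded as "events result in a low level of inconvenience or concern with the therapeutic measures", and may also involve some loss of function.
- The severe grade covers cases where "events interrupt a patient's usual daily activity and may require systemic drug therapy or other treatment", and such events are as a rule incapacitating.
- Life threatening means that the patient is "at immediate risk of death from the reaction as it occurred".

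Attribution has two categories and covers all adverse events. An event is *associated* if "The event is temporally related to the administration of the study product and no other etiology explains the event". It is *not associated* if the timing does not fit, or if another cause seems to account for it, or both. The same section states that the product should always be under suspicion, and that events are documented whatever their attribution.

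Under Reporting Procedures, SAEs go to the IRB within 10 days. Unexpected deaths or life-threatening experiences that are "related to research which be reported to the UTMB IRB within 2 days" have the shorter limit.

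**The concern.** The participants are infants born at 30 weeks or less, in intensive care and fed by gavage. They have no daily activities to interrupt and cannot report inconvenience. If the grading words do not describe them, two clinicians can grade the same event differently with nothing in the protocol to settle it. Section 4.0 says that nurses and parents are blinded and states no blinding for the clinician who grades. It also assigns groups in a repeating 1-2-3 order. A loosely anchored grade is more exposed to knowledge of dose under those conditions.

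The causality rule has a direction. Sick preterm infants often have another candidate cause for an event, and all three groups receive L-citrulline, so no untreated group can show which labels are wrong. Section 1.0 says the side-effect profile in preterm infants is unknown. At stake is the usefulness of the severity and attribution data, and possibly the speed of some IRB reports.

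**Working it through.** **1. The plan's own safety figure.** Section 4.0 gives power 0.92 for an equivalence test of mean blood pressure: 11 per group, SD 10 mmHg, limits ±15 mmHg, true difference 0, level 0.05. The standard error is 10 × √(2/11) = 4.264 mmHg, with 20 degrees of freedom. Exact power of the two one-sided t-tests, integrating over the sample SD, is 0.920. The figure reproduces. It uses neither a severity grade nor an attribution, so this point does not touch it.

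**2. The general severity scale, anchor by anchor.**

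| Grade | Activity-type anchor | Treatment anchor | Other |
|---|---|---|---|
| Mild | no interference with activities | little or none | – |
| Moderate | inconvenience; some loss of function | no threshold given | concern over therapy |
| Severe | activity interrupted; usually incapacitated | may need a drug or other treatment | – |
| Life threatening | – | – | immediate risk of death |

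The second column has no clear meaning for these infants. Without it, life threatening is intact, mild means little or no treatment, moderate has no treatment content of its own, and severe means that treatment may be needed. Take a modest rise in supplemental oxygen. One clinician can call that minimal treatment (mild); another can call it treatment other than a drug (compatible with severe). The usual way to decide would be whether the patient was incapacitated, which is one of the anchors that does not apply.

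**3. The causality rule as a table.**

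| Timing fits? | Another cause seems to explain it? | Label |
|---|---|---|
| Yes | No | associated |
| Yes | Yes | not associated |
| No | No | not associated |
| No | Yes | not associated |

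The second row matters. A well-timed event is moved to *not associated* by an apparent alternative, even if the product may have contributed. There is no intermediate category. The principle that the product stays under suspicion has no working rule attached to it.

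**4. Size of the tilt: illustration on assumed inputs only.** Let *p* be the share of infants with a true reaction, and *q* the chance that another cause seems to explain it. Neither is in the documents. The chance that a group of 14 shows at least one *associated* reaction is 1 − (1 − p(1 − q))^14. With p = 0.20:

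- q = 0: 1 − 0.80^14 = 0.956
- q = 0.25: 1 − 0.85^14 = 0.897
- q = 0.50: 1 − 0.90^14 = 0.771
- q = 0.75: 1 − 0.95^14 = 0.512
- q = 0.90: 1 − 0.98^14 = 0.246

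The direction follows from the wording. The size is set by the choice of *q*.

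**5. Reporting.** If the attribution label decides whether a life-threatening event counts as research-related, relabelling would move its limit from 2 to 10 days, at most 10 − 2 = 8 days later. The protocol does not expressly make that link.

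**The case against.** The strongest reply is that little in the plan rests on these labels. Section 9.0 names no analysis by severity grade or attribution. Blood pressure is the only powered safety endpoint. Events are captured whatever their attribution, with description, onset and resolution, so all-cause counts by dose group are not biased by the rule. Platelets below 50,000, intraventricular haemorrhage of grade III or more, and enterocolitis or retinopathy needing surgery are SAE criteria outside the general scale, as is the blood pressure threshold for withdrawal. Glucose, electrolytes and blood counts remain measured values. All of this stands and limits the point.

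It is also fair that treatment need is part of the mild and severe grades and that life threatening uses no activity anchor, so the scale is not empty. A competing cause being present is not the same as its appearing to explain the event, and the causality definitions are offered as guidance.

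What does not stand is that the labels therefore need no repair. Section 7.0 makes both mandatory for every event. Readers of a first study in this population will look at them, and the defect is in a stated rule rather than in missing detail.

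**Conclusion.** The point holds in limited form and is a cheap improvement. The general mild, moderate and severe anchors largely do not apply to this population, and what remains does not clearly separate the grades. The causality rule, for all adverse events including hypotension, tilts towards *not associated*. That rests on the wording plus one assumption: that these infants often have another apparent cause for an event.

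A reader might infer more, without support from the documents:

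- *That Aim 2 as a whole is unreliable.* Blood pressure, all-cause capture and the listed thresholds do not depend on the general grade.
- *That a stated fraction of true reactions would be lost.* Assuming that 50–90% have a competing explanation and reporting a 50–90% loss only restates the assumption.
- *That a misattributed life-threatening event certainly moves to the 10-day route.* The reporting text is not tied to the attribution label, so it may do so. Some text of Section 7.0 between the SAE list and the reporting procedures was not available, so a further review step cannot be excluded.

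**What to change.** 1. Replace the general mild, moderate and severe anchors with neonatal ones based on the change in monitoring or care that the event led to. Add one line each on what the grades mean for respiratory, metabolic and blood-count events. Without those lines, a care-based scale would depend on the assessor just as much.
2. Reword the causality rule so that a temporally related event is *associated* when there is a reasonable possibility that the product contributed, rather than only when nothing else explains it. Going further, to *associated* unless another cause is confirmed, would reverse the tilt and class much background illness as drug-related.
3. State in Section 9.0 that all adverse events will be summarised by dose group, whatever their attribution, as the main adverse event comparison. The planned data already allow this.

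The cost is protocol and CRF wording. The downside is that more events will be labelled associated, and some may then be reported on the 2-day route.

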## Specific Aim 2 -

To determine the safety of oral L-citrulline supplementation in premature infants. Increased production of NO may lead to systemic hypotension by its vasodilator effect. All infants in the neonatal ICU are always on electronic monitors and monitored for heart rate, oxygen saturations and BP. We will continuously monitor all infants for systemic hypotension. Significant hypotension will be defined as a 25% drop in systemic mean blood pressure (measure by non-invasive blood pressure monitoring). Other parameters to be recorded include increase in oxygen requirements/escalation in respiratory support, metabolic abnormalities (on routine glucoses and electrolyte monitoring), effect on bone-marrow by weekly complete blood counts (done routinely on preterm infants).

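### Hypotension that two inotropes hold below a 25% fall in MAP is graded no higher than Moderate and meets no specific SAE or withdrawal criterion

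*Combined protocol and SAP*

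**What the plan says.** The grading system in section 7.0 sets the three lower grades by percent fall in MAP from baseline: Mild up to 10%, Moderate up to 25%, and then "Severe: Drop in mean arterial pressure (MAP) > 25% from baseline". Only the top grade mentions treatment: "Life threatening: Severe hypotension requiring 2 or more inotropes (Dopamine, Epinephrine, Norepinephrine".

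Section 7.0 also has a general severity scale, whose Severe category does mention drug therapy. It is kept for other events: "For events not included in the protocol defined grading system, then the following guidelines will be used to quantify intensity".

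The SAE list in section 7.0 has a general condition, "Life-threatening event (defined as a subject at immediate risk of death at the time of the event", and a specific one, "significant hypotension requiring 2 or more inotropes". Specific Aim 2 supplies the meaning of the adjective: "Significant hypotension will be defined as a 25% drop in systemic mean blood pressure". Section 7.0 repeats that definition and takes the average MAP over the week before dosing as baseline.

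Section 8.0 withdraws an infant for a MAP fall above 25%, with no reference to treatment. Section 6.0 places no limit on concomitant drugs, and section 3.0 leaves management to the treating team. On AE data, section 7.0 states: "Information to be collected includes event description, time of onset", followed by severity, relationship to study product and resolution. Treatment given for the event is not named.

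**The concern.** Systemic hypotension is the one immediate systemic risk that the protocol names: "Increased NO production may theoretically lead to systemic hypotension". A severity grade should reflect how ill the infant was. MAP measured under vasoactive support partly reflects the support. Nothing in the visible text defines MAP as the untreated value, and nothing asks clinicians to wait for a 25% fall before treating. Prompt and effective rescue can therefore lower the recorded grade.

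The sharpest case is an infant who needs two inotropes. The protocol regards that need as a mark of life-threatening illness, but only if the pressure also fell by more than 25%. If the inotropes keep it above that line, the event shares a grade with an untreated fall of the same size. What is at stake is consistent classification and escalation of the main named hazard, in a population in which the protocol says the drug has not been studied before.

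**Working it through.** The documents give no figure for this point. The nearest is the power of 0.92 for the blood-pressure equivalence test in section 4.0 (11 per group, SD 10 mmHg, limits of ±15 mmHg, true difference 0). Two one-sided t tests at 0.05 with 20 degrees of freedom, simulated with 2,000,000 draws, give 0.920, so that figure reproduces. Nothing below depends on it.

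**Step 1: the rule as written.**
- Fall above 25% with two or more inotropes: Life threatening.
- Fall above 25% otherwise: Severe.
- Fall above 10% and up to 25%: Moderate.
- Fall up to 10%: Mild.

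Read literally, Moderate also contains Mild, but the intended band is clear.

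**Step 2: apply the rule.** The last column uses the change proposed below, and assumes that the two inotropes are newly needed for blood pressure after the first dose.

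| MAP fall | 0 inotropes | 1 inotrope | 2 inotropes | 2 inotropes, proposed |
|---|---|---|---|---|
| 8% | Mild | Mild | Mild | Life threatening |
| 15% | Moderate | Moderate | Moderate | Life threatening |
| 20% | Moderate | Moderate | Moderate | Life threatening |
| 25% | Moderate | Moderate | Moderate | Life threatening |
| 26% | Severe | Severe | Life threatening | Life threatening |
| 30% | Severe | Severe | Life threatening | Life threatening |

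Up to a 25% fall, treatment never changes the current grade.

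**Step 3: look for another explicit rule that catches a 24% fall on two inotropes.**
- General severity scale: does not apply, because hypotension has its own grading system.
- Specific hypotension SAE criterion: not met, because 24% is below the 25% that defines significant. The SAE definition (a 25% drop) and the Severe grade (above 25%) differ only at exactly 25%.
- Blood-pressure withdrawal criterion: not met, because it needs more than 25%.
- General SAE condition: met only if the infant is judged to be at immediate risk of death.
- Section 7.0, Reporting Procedures: an event that the investigator considers serious must be submitted on the SAE form.
- Section 8.0: the treating investigator may withdraw the infant in the infant's best interest.

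The last three can catch the case. All rest on judgment, and none changes the grade.

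**Step 4: scale.** The documents give no rescue rate, so the number of infants affected cannot be estimated and may be zero. With the planned 14 per group, one reclassified infant moves that group's proportion by 1/14 = 7.1 percentage points. That describes the group size. It is not an estimate of the effect of the definition.

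**The case against.** The strongest reply is that the case is narrow and already has safeguards. Section 7.0 asks for changes in severity and intermittent episodes to be documented, so an excursion above 25% before rescue works is already Severe and meets the withdrawal rule. What remains is an infant, off TPN for at least 3 days, who is given two inotropes although MAP never fell by more than 25%. The judgment routes in step 3 could escalate that infant. An objective MAP threshold is also a defensible choice, because rescue is decided by the treating team and may have causes such as sepsis. All of this stands. It limits the size of the point but does not give the infant the right grade.

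A reader might infer more than the documents support:

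- **Reporting is delayed from days to months.** SAEs go to the IRB within 10 days, or 2 days for an unexpected death or life-threatening experience related to research, while the DSMB looks every 4 months. But part of section 7.0 was not available. Section 6.0 refers to section 7.0 for toxicity handling, and section 9.0 refers to it for the DSMB. Neither provision is in the visible text, so the delay cannot be fixed. The 2-day route would in any case still depend on relatedness.
- **Rescue could never be seen in the data.** The AE items are introduced as inclusions, the event description is one of them, and section 5.0 collects detailed data from the electronic medical record. Rescue can be retrieved. It is only not prespecified.
- **The dose comparison of safety is biased.** Section 9.0 plans no comparison of graded AEs by dose, so no planned test uses these grades.
- **Any vasoactive start should count as Severe.** That would tie the grade to treating-team practice when blinding is stated only for nurses and parents. It is a debatable trade-off and is not proposed here.

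**Conclusion.** The point holds in a limited form. In the visible text, an infant kept below a 25% MAP fall by two inotropes is graded Moderate or Mild and lies outside the specific SAE criterion and the blood-pressure withdrawal criterion. Escalation depends on judgment. This follows from the rule as stated; it is not a matter of missing detail.

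The consequence is small: it concerns classification, the affected number is unknown, and with no early-stopping rule in section 8.0 an SAE report would not by itself halt enrolment. The conclusion rests on reading significant as defined in Specific Aim 2 and section 7.0, and on the visible text. The grading list itself is complete there. Rating: minor, a cheap improvement.

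**What to change.** 1. In section 7.0, define Life-threatening hypotension, and the matching SAE, as a new need for two or more inotropes for blood pressure after the first dose, whatever the percent fall in MAP.
2. In section 8.0, add the same condition as a withdrawal criterion beside the existing rule for falls above 25%. Grade, SAE and withdrawal then agree.
3. Keep the Mild, Moderate and Severe MAP thresholds as they are. Starting a single drug does not change the grade.
4. Add one AE-form item, filled from the electronic medical record, for any vasoactive drug or volume bolus given for blood pressure, with the reason.
5. Report three counts by dose group and to the DSMB: MAP fall above 25%, rescue only, and either.

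The cost is three wording changes (grade, SAE, withdrawal), one form item and a short table, with no new samples or visits. A few more SAE reports may follow, and an infant newly on two inotropes would now stop study drug. Deciding that inotropes were needed for blood pressure still takes judgment, and rescue may have other causes. That is why the reason is recorded and the MAP-only count is kept alongside.
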